## **C2. Power Considerations:**

The goal is to enroll 100 subjects for each of the six brands listed in Table 2. The mean toxicant uptake level is expected to vary between brands; however, the standard deviation (SD) should

be similar for all brands. This is the common SD and is equivalent to the root of the Mean Square Error (MSE) from the one-way ANOVA. With a total of 600 subjects, this F-test will have 92% power to detect a significant difference at the 0.05 level if the brands with the largest and smallest means differ by at least one-half the common SD. Therefore, if the common SD for the biomarker was 10 units, then there would be a 92% chance that we find a significant difference between brands if the biggest and smallest means were at least 5 units apart. This analysis was done using Power Analysis and Sample Size (PASS) 2005 by NCSS, Inc.

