### **C. Statistical analyses**

#### **C1. Analytic Approach**

##### ***Primary Aims***

1. To determine the toxicant exposure associated with currently marketed oral tobacco products with varying levels of toxicants and nicotine.

Subject characteristics will be examined across sites and ST users at each site will be compared to the characteristics of the respective state population of ST users. The outcomes for this study are the uptake of toxicants, as measured by biomarkers of exposure including NNAL, NNN, nitrosoamino acids,

1-HOP and total nicotine equivalents and biomarkers of effect such as CVD risk factors. The distribution of each biomarker will be examined to determine if a data transformation is necessary. From our previous experience, the distributions of many biomarkers are often skewed with a long right tail and need to be analyzed in the natural log scale. The two biomarker assessments for nicotine from each subject will be used to evaluate the reliability, as measured by the intraclass correlation. The two readings will then be averaged for the subsequent analysis. The geometric mean and the corresponding 95% confidence interval for the biomarkers will be calculated for each brand. The one-way analysis of variance (ANOVA) will be used to compare the mean toxicant levels between all six brands. If this global test is significant, then the Tukey's studentized range procedure will be used for pair-wise comparisons between brands, while maintaining an overall significance level of 5%.

2. To determine if toxicant and nicotine exposure is related to product factors such as the levels of these constituents (nicotine, NNK and NNN) in the products and patterns of use such as tins per week, dips per day, duration per dip, total dip duration (dip per day x duration per dip), weight per dip.

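### C2 ties the 92% power only to a half-SD gap between the extreme brand means; 92% is the evenly spaced case, and the minimum at that gap is 78%

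*Combined protocol and SAP*

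**What the plan says.** The power statement is in section C2 (Power Considerations) and concerns the global test of Primary Aim 1 in section C1: "The one-way analysis of variance (ANOVA) will be used to compare the mean toxicant levels between all six brands".

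- Sample size: "The goal is to enroll 100 subjects for each of the six brands listed in Table 2".
- Power and level, with all 600 enrolled: "this F-test will have 92% power to detect a significant difference at the 0.05 level if the brands with the largest and smallest means" are far enough apart.
- Condition: "if the brands with the largest and smallest means differ by at least one-half the common SD".
- Definition of the SD: "This is the common SD and is equivalent to the root of the Mean Square Error (MSE) from the one-way ANOVA".

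C2 then illustrates the claim with a common SD of 10 units, for which it gives a "92% chance that we find a significant difference between brands if the biggest and smallest means were at least 5 units apart". It names PASS 2005 as the software but not the set of means that was entered. Neither C2 nor any other section says where the four brands between the extremes are assumed to lie.

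**The concern.** The condition in C2 involves only the two extreme means, and its at-least wording, used in both the statement and the example, turns 92% into a guarantee for any set of six means with that range. The F-test does not have that property. Its power depends on how far all six means spread around their average, so two sets of means with the same range can give quite different power.

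This is the only power figure in the document, and it supports the first primary aim. Under C1 the Tukey pairwise comparisons follow only if the global test is significant, so a missed global test ends the brand comparison for that biomarker. The same test is applied to several biomarkers, whose patterns of brand means need not be alike. A non-significant result could then be read as 92% assurance against a half-SD difference when the assurance for that pattern is lower.

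**Working it through.** **Inputs, from C1 and C2.** Six brands; n = 100 per brand; N = 600; alpha = 0.05; range of means d = 0.5 in units of the common SD. C2 gives no dropout allowance, so 100 per brand is taken as evaluable.

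**Formula.** With means μ₁ to μ₆ in SD units and average μ̄, let S = Σ(μᵢ − μ̄)². The noncentrality is λ = n × S. Power is the probability that a noncentral F with 5 and 594 degrees of freedom and noncentrality λ exceeds the 5% critical value, 2.229.

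**Step 1: reproduce the plan's figure.** For means 0, 0.1, 0.2, 0.3, 0.4 and 0.5, μ̄ = 0.25 and S = 2 × (0.25² + 0.15² + 0.05²) = 0.175. Then λ = 17.5 and power = 91.6%, which rounds to the stated 92%.

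**Step 2: keep the range at 0.5 SD and move the inner means.**

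| Pattern of the six means (SD units) | S | λ | Power |
|---|---|---|---|
| 0, 0.25, 0.25, 0.25, 0.25, 0.5 (four at midpoint) | 0.125 | 12.5 | 78.4% |
| 0, 0.15, 0.25, 0.25, 0.35, 0.5 (milder clustering) | 0.145 | 14.5 | 84.9% |
| Evenly spaced | 0.175 | 17.5 | 91.6% |
| 0, 0, 0, 0, 0, 0.5 (one brand apart) | 0.208 | 20.8 | 95.9% |
| 0, 0, 0.25, 0.25, 0.5, 0.5 | 0.250 | 25.0 | 98.4% |
| 0, 0, 0, 0.5, 0.5, 0.5 (three versus three) | 0.375 | 37.5 | 99.9% |

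**Step 3: show that the first row is the minimum.** Wherever μ̄ lies, the two extreme means alone contribute at least 2 × (d/2)² = d²/2 to S, and the other four contribute at least zero. Both bounds are met when the four inner means are at the midpoint. So S cannot be below 0.5²/2 = 0.125, and power at a range of 0.5 SD cannot be below 78.4%.

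**Step 4: find the range that secures 92% for any pattern.** In the least favourable pattern λ = 100 × d²/2 = 50d². Power reaches 92% at d of about 0.595. At d = 0.60, λ = 50 × 0.36 = 18.0 and power = 92.4%.

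**Step 5: see how typical a shortfall is.** As an illustration only, the four inner means were drawn uniformly between the extremes 20,000 times. Median power was about 94% and the mean about 93%. About 37% of draws were below 92%, about 6% below 85% and about 0.3% below 80%.

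**The case against.** The strongest reply is that the 92% reproduces under a conventional choice of means, that exactly 78% needs four brands to coincide at the midpoint, and that the typical pattern in Step 5 has slightly more than 92%. The products were also chosen to cover a range of nicotine and nitrosamine levels (section B2d), so four coincident midpoint brands are not what the design leads one to expect. All of this stands. It makes 78% a worst case and not a forecast. It does not rescue the wording of C2, which claims 92% for every pattern with the stated range, while over a third of the random patterns fall short.

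A reader might infer two stronger things.

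- *That 92% holds only if the six means are evenly spaced.* It does not. Any pattern with S of at least 0.175 does as well as even spacing or better, as the last three rows of the table show.
- *That the 10-unit example is on the wrong scale, because C1 expects that many biomarkers "need to be analyzed in the natural log scale".* The documents do not support this. C1 leaves the transformation to be decided for each biomarker after its distribution is examined. The C2 condition is in SD units and applies on whichever scale is analysed. The example is hypothetical and names no scale. Restating it as a ratio of geometric means would need a log-scale SD that the documents do not give.

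**Conclusion.** The point holds as an unstated assumption behind the plan's only power figure. The number is computed correctly for evenly spaced means, but C2 presents it as following from the range alone. At a range of exactly 0.5 SD, power can lie anywhere from 78.4% to 99.9%, depending on the other four means. The chance of missing the difference can therefore be as high as about 22%, against the 8% that C2 implies. Nothing here shows that the trial is underpowered or that the sample size is wrong.

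These figures assume 100 evaluable subjects in every brand, a common SD, and biomarkers measured in all 600 subjects. The shares in Step 5 also depend on the uniform placement of the inner means, which is an illustration and not taken from the documents.

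**What to change.** Restate the power sentence in C2 along these lines:

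> With 100 evaluable subjects per brand and a common SD, the F-test at the 0.05 level has 92% power if the extreme brand means differ by 0.5 SD and the six means are evenly spaced. The minimum power for any pattern of means at a range of 0.5 SD is 78%. At least 92% is assured for any pattern when the range is 0.60 SD.

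Qualify the example in the same way. With an SD of 10 units, a 5-unit range gives 92% for evenly spaced means and no less than 78% otherwise; a 6-unit range (0.60 × 10) gives at least 92% for any pattern.

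The cost is a few sentences in C2 and a less favourable headline figure. Sample size, endpoints and analysis stay as they are.

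### C2's 92% power matches six equally spaced brand means, which C2 does not state; the condition it does state (range of at least 0.5 SD) guarantees only 78%

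*Combined protocol and SAP*

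**What the plan says.** Section C2 (Power Considerations) sets the recruitment target: "The goal is to enroll 100 subjects for each of the six brands listed in Table 2". It then gives the plan's only power statement: "With a total of 600 subjects, this F-test will have 92% power to detect a significant difference at the 0.05 level", subject to one condition, "if the brands with the largest and smallest means differ by at least one-half the common SD". A worked example repeats the claim with a common SD of 10 units: a "92% chance that we find a significant difference between brands if the biggest and smallest means were at least 5 units apart". C2 takes the SD to be common to all brands and names the software (PASS 2005). It does not say what pattern of means was entered.

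The test in question is the global comparison under the first primary aim in C1: "The one-way analysis of variance (ANOVA) will be used to compare the mean toxicant levels between all six brands". Pairwise comparisons follow conditionally: "If this global test is significant, then the Tukey's studentized range procedure will be used for pair-wise comparisons between brands".

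**The concern.** The power of a one-way ANOVA F-test depends on the spread of all the group means, not only on the gap between the highest and lowest. Two sets of six means with the same range can give quite different power. C2 fixes the range, leaves four of the six means free, and still attaches a single figure to every case in which the range is at least 0.5 SD. That cannot be right unless 92% is the figure for the least favourable pattern.

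C2 is the only quantitative support for the sample size. A reader who takes it at face value will put the chance of missing a 0.5 SD range at no more than 8%. If that chance can be materially larger, a non-significant global test could be taken as better evidence than it is that no two brands differ by half an SD.

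**Working it through.** **Inputs (C1 and C2).** Six brands, 100 subjects each, so degrees of freedom are 5 and 600 − 6 = 594. Alpha is 0.05. The range of the means is 0.5 SD (5 units with SD 10). The positions of the four middle means are not given.

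**Formula.** With means μᵢ in SD units and μ̄ their average, the noncentrality parameter is λ = 100 × Σ(μᵢ − μ̄)². Power is the probability that a noncentral F(5, 594, λ) variable exceeds the 5% critical value, F(0.95; 5, 594) = 2.229.

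**Step 1: reproduce the stated figure.** Equally spaced means over 0.5 SD are 0.1 SD apart and deviate from their average by ±0.05, ±0.15 and ±0.25.
- Σ = 2 × (0.0025 + 0.0225 + 0.0625) = 0.175
- λ = 17.5, power 91.6%, which rounds to C2's 92%

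**Step 2: find the minimum under the stated condition.** For a fixed range, the two extremes contribute at least 2 × 0.25² = 0.125 to the sum of squares whatever the centre. The other four contribute nothing only when they sit at the midpoint. That pattern is therefore the least favourable.
- λ = 100 × 0.125 = 12.5, power 78.4%
- A simulation of 20,000 trials gave 78.3%

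**Step 3: other patterns with the same 0.5 SD range.**

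| Pattern of means | λ | Power |
|---|---|---|
| Four at the midpoint (minimum) | 12.5 | 78.4% |
| Four at 0.1 SD above the lowest | 15.5 | 87.5% |
| Equally spaced | 17.5 | 91.6% |
| One against five | 20.8 | 95.9% |
| Two against four | 33.3 | 99.8% |
| Three against three (maximum) | 37.5 | 99.9% |

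Of these, only equal spacing reproduces 92%. Any pattern with λ of about 17.7 or more reaches it.

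**Step 4: what would make 92% a guarantee.** In the least favourable pattern with range r, λ = 100 × r²/2.
- Setting this to 17.73 gives r = √0.3546 = 0.595 SD. Rounded up to 0.60 SD, λ = 18.0 and power is 92.4%.
- Holding the range at 0.5 SD instead would need 142 per brand (λ = 142 × 0.125 = 17.75), which is 852 in total.

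**The case against.** The strongest reply is that nothing in C2 is miscalculated. Equal spacing is a standard planning pattern, it gives the stated 92%, and the 78% case requires four of six brands to sit exactly midway between the other two. That corner is unusual. When the four middle means are drawn uniformly within the range (an assumption), average power is 93% and about 63% of patterns reach 92%.

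The plan's own product data point the same way. Averaging the available Table 2 values within each of its six groups and scaling those averages to a 0.5 SD range gives 92.3% for nicotine and 92.8% for NNK plus NNN. Taking logs of the group averages first gives 94.7% and 87.6%. These are product contents, not uptake, and some cells are blank, but every figure is well above 78%. C1 also requires a geometric mean and 95% confidence interval for each brand, so precision will be visible whatever the planned power.

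Most of this stands. It shows that 92% is a reasonable planning figure and that 78% is a floor, not a forecast. It does not rescue the sentence in C2, which states no pattern and claims 92% for any range of half an SD or more. The log-scale NNK plus NNN pattern, at 87.6%, already falls short of that claim.

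A reader might go further and treat the Tukey step as part of the error. At 0.5 SD the Tukey comparison of the two extreme brands has about 75% power, and requiring a significant F-test first lowers this to about 72% in the least favourable pattern. But C2 claims power only for the F-test, so these figures contradict nothing. Running Tukey only after a significant F-test is valid and conservative: simulated family-wise error under the null is about 3.8% with the requirement and 5.1% without it.

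**Conclusion.** The point holds as a matter of what C2 guarantees. On its stated condition, F-test power is at least 78.4%, not 92%. The shortfall is up to about 14 percentage points, and the chance of a miss at a 0.5 SD range is up to 22% instead of 8%. The 92% belongs to equally spaced means, an assumption C2 leaves out.

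Three stronger readings are not supported:
- That 92% is reached only with equal spacing. Several other patterns exceed it, up to 99.9%.
- That the study's power is 78%. This is the lower bound at a 0.5 SD range; the likely figure depends on uptake means the documents do not give.
- That the software run was wrong. The match suggests equally spaced means were entered, but this is an inference; C2 does not say so.

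The figures assume normal errors on the analysis scale, a common SD, and 100 evaluable subjects in every brand. C2 makes no allowance for losses; with fewer subjects, or unequal numbers at the same total, the guaranteed minimum would be lower.

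**What to change.** Restate the power claim in C2 along these lines:

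> With 100 evaluable subjects per brand, the F-test at the 0.05 level has about 92% power if the six means are equally spaced over a range of 0.5 SD, at least 78% for any pattern with that range, and at least 92% for any pattern once the range is 0.60 SD.

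Change the worked example to match. With an SD of 10 units, a range of 5 units gives about 92% if the means are equally spaced and at least 78% otherwise; a range of 6 units gives at least 92% for any pattern. State the pattern of means entered in the software.

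The cost is wording only. No subjects, visits or assays are added and no analysis changes, though the stated power becomes less favourable. Running Tukey's procedure without first requiring a significant F-test is an optional improvement. It would change the testing procedure, so it should be decided separately.
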